1. SUMMARY

Rationale: A fecal immunochemical test (FIT)-based colorectal cancer (CRC) screening program was implemented in the Netherlands in 2014. Nearly 15,000 patients are yearly diagnosed with a *large complex (non-pedunculated) colorectal polyp* (LNPCP) for which endoscopic resection is the first-line therapy. LNPCPs carry a high malignant potential. Endoscopic resection of LNPCPs is technically challenging, with a risk of local recurrence, repeat colonoscopy and additional surgery, resulting in a negative impact on clinical outcome, patient's quality of life, and increased colonoscopy burden for repeat procedures.

Objective: Development of a standard training program for advanced endoscopic resection techniques is urgently needed to improve outcomes at both a patient and program level. Improvement of *education* and *colonoscopy training* is the first key-step.

- (I) **A.** To develop a systematic training program for treatment of LNPCPs
- B.** To investigate if additional training improves clinical outcomes
- (II) To assess the impact of performing endoscopic resection for LNPCPs on the patients quality of life (QoL).
- (III) To perform an economic analysis comparing post-training endoscopic resection vs. common endoscopy practice vs laparoscopic surgery.

We hypothesize that a series of measures, i.e. *a priori* endoscopic and histological diagnosis followed by a therapeutic plan and high-quality endoscopic resection performance will improve outcome.

Study design: A multicenter randomized controlled trial (RCT) will be conducted to compare the performance of additionally trained endoscopists (n=15 centers, n=30 endoscopists) vs. regularly trained endoscopists (control group; n=15 centers, n=30 endoscopists).

The period of inclusion and follow-up will be from 2019-2021, where the duration of the follow-up of an individual patient will be 6 months, confirm the current guidelines.

Study population: Patients (18 years and older) who have an indication for colonoscopy, in particular patients from the nationwide screening program.

Inclusion criteria for participating endoscopists will be:

1. Experienced endoscopists (i.e. total number of colonoscopies performed will be at least 250 procedures under supervision plus 500 colonoscopies independently) including documentation of the key-performance indicators (cecal intubation rate, adenoma detection rate and polypectomy rate)

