After correction for the design effect ($= 1+(m-1)*ICC$, where $ICC = 0.025$ and the mean number of patients per colonoscopist is 35, i.e. $m = 35$), 10% loss in efficiency due to the variation in the number of colonoscopies performed during the study period per colonoscopist (3), and a 20% drop-out risk for patients with LNPCP, the number of LNPCP cases required to detect a difference of 10% (20% local recurrence in the control group vs 10% in the intervention group) with a power of 90% and using a significance level alpha of 5% is 683 per group. This means that 20 colonoscopists per group are required. In the revised protocol, we have increased the power of analyses from 80% to 90%. In conclusion, in the 20 participating centers (10 per arm), a total of 20 colonoscopists will perform approximately 35 endoscopic resections each over 1.5 year.

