4.2 Randomisation, blinding and treatment allocation

Participating centers will be randomized to the *intervention group* vs. *control group*, as detailed in **Figure 1**. To mitigate the effect of contamination, i.e. exchange of knowledge, practical skills between participants, we prefer to randomize centers instead of endoscopists. In each center, two endoscopists will participate in the study. Both the control (n=30 endoscopists) and the intervention group (n=30 endoscopists) will receive an e-learning module regarding the OPTICAL I model focused on optical diagnosis of T1 carcinomas, and assessment of an EMR scar to recognize recurrence. In addition to this, the intervention group will receive an additional EMR training package, consisting of an e-module and a two-day symposium.

We will target our intervention (training) to this specific group because endoscopists at the beginning of their career may be more compliant to implement a change in their practice. An additional questionnaire will be used to provide baseline information regarding total number of endoscopic resections over the past year, resection techniques used (EMR vs ESD), the complication rate (bleeding, perforations) and the referral rate to surgery in order to select 20 endoscopists with comparable experience and endoscopic proficiency. We realize that such selection is associated with difficulty – baseline characteristics among the 2 groups will never be the same. Evaluation of such baseline information is, however, of importance for a meaningful interpretation of the study outcomes.

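### Section 3.1.4 requires 20 colonoscopists per group but concludes with 20 in total, and the protocol leaves open whether 20 or 30 centres are randomised

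*Protocol*

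**What the plan says.** The protocol gives the size of the trial in several places.

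- **3.1.4, requirement.** For "20% local recurrence in the control group vs 10% in the intervention group", the number of lesions "with a power of 90% and using a significance level alpha of 5% is 683 per group". The text goes on: "This means that 20 colonoscopists per group are required".
- **3.1.4, conclusion.** The section closes with "in the 20 participating centers (10 per arm), a total of 20 colonoscopists will perform approximately 35 endoscopic resections each over 1.5 year".
- **3.1.4, per centre.** Two colonoscopists take part in each centre, with at least 35 lesions each and so 70 per centre. The Summary and 4.2 also set two per centre.
- **Summary.** The trial compares "additionally trained endoscopists (n=15 centers, n=30 endoscopists") with a control group of the same size. That makes 30 centres and 60 endoscopists.
- **Section 3 and 4.3.2.** Section 3 has at least 30 trained endoscopists against 30 controls; 4.3.2 refers to the 30 endoscopists of the intervention group.
- **4.2.** "Both the control (n=30 endoscopists) and the intervention group (n=30 endoscopists) will receive an e-learning module". The next paragraph describes a baseline questionnaire used "in order to select 20 endoscopists with comparable experience and endoscopic proficiency", without saying whether that number is per group or overall.

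**The concern.** The number of randomised centres, the number of endoscopists and the recruitment target are basic design facts, and the protocol does not fix them. Three totals can be read from it: 20, 40 or 60 endoscopists. The smallest stands in the sentence that sums up the sample size section, and it is half of what that section has just derived.

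The sizes differ in power for the primary endpoint, local recurrence at 6 months. They also differ in how many sites and training places are needed. With three sizes in the text, a final count of 20, 40 or 60 endoscopists could each be reported as the planned number, so a shortfall could not be recognised.

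**Working it through.** **Inputs, all from 3.1.4:** recurrence 20% against 10%; alpha 5%; power 90%; ICC 0.025 at colonoscopist level; 35 lesions per colonoscopist; 10% efficiency loss for unequal cluster sizes; 20% drop-out. Sidedness is not given ("using a significance level alpha of 5"%). Two-sided is assumed because only that reproduces the stated figure; one-sided testing with the same inflation gives 550 to 609 per group.

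**Step 1. Reproduce the requirement.** With p̄ = 0.15 and pooled variance under the null:

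n = [1.960 × √(2 × 0.15 × 0.85) + 1.282 × √(0.2 × 0.8 + 0.1 × 0.9)]² / 0.1² = 266 per group.

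Design effect = 1 + (35 − 1) × 0.025 = 1.85.

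266 × 1.85 = 492.1; 492.1 / 0.90 / 0.80 = 683.5, against 683 stated.

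683 / 35 = 19.5, so 20 colonoscopists per group. The protocol's calculation is reproduced, and drop-out sits inside the 683 that is divided by 35.

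**Step 2. Lesions under each stated size.** The requirement is 2 × 683 = 1,366.

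- 20 colonoscopists in total: 20 × 35 = 700
- 20 per group: 40 × 35 = 1,400
- 30 per group: 60 × 35 = 2,100

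Twenty centres at 70 lesions each also give 1,400, so the closing sentence of 3.1.4 does not agree with its own number of centres.

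**Step 3. Power by the same method.** For k colonoscopists per arm, effective n = k × 35 × 0.80 × 0.90 / 1.85, and power = Φ{[0.1√n − 1.960 × √0.255] / √0.25}.

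| Colonoscopists per arm | Lesions per arm | Effective n | Power |
|---|---|---|---|
| 10 | 350 | 136.2 | 63.9% |
| 20 | 700 | 272.4 | 90.7% |
| 30 | 1,050 | 408.6 | 98.0% |

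**Step 4. How far the lowest figure depends on the reading (10 per arm).**

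- Drop-out applied, no efficiency loss: 350 × 0.80 / 1.85 = 151.4, power 68.5%.
- Design effect based on the 28 analysed (1 + 27 × 0.025 = 1.675): 252 / 1.675 = 150.4, power 68.2%.
- 35 already net of drop-out: 350 × 0.90 / 1.85 = 170.3, power 73.6%.
- 35 net of drop-out and no efficiency loss: 350 / 1.85 = 189.2, power 78.0%.

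No reading of a 20-colonoscopist trial reaches 90%.

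**The case against.** A reader might infer that the trial is planned with 10 colonoscopists per arm and is therefore underpowered at 64%. The documents do not support that. No section states 10 colonoscopists per arm. The closing sentence of 3.1.4 has 10 centres per arm, and at two colonoscopists per centre that is 20 per arm, exactly what the derivation requires. A team opening those 20 centres with two endoscopists each would have about 1,400 lesions, above the 1,366 needed. The sections that describe how the trial is run give 30 per arm, or at least 30, where power is about 98%. The total of 20 is most likely a slip.

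It can also be said that a requirement of 20 per group and a plan of 30 per group need not conflict, since a trial may plan above its minimum. That is fair for the endoscopist numbers, although 3.1.4 never presents 20 as a minimum beneath a larger plan. It does not explain 10 centres per arm in 3.1.4 against 15 in the Summary. The selection of 20 endoscopists in 4.2 is ambiguous and is weak evidence for a trial of 20 in total.

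The single figure of 64% depends on taking 35 as the number before drop-out. The 683 / 35 step supports this, but an earlier sentence in 3.1.4 can be read as making 35 already net of drop-out. The range of 64% to 78% should be quoted.

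Finally, a reader might want to judge the sizes with a design effect at centre level. If the ICC of 0.025 is assumed to apply to centres of 70 lesions, the design effect is 1 + 69 × 0.025 = 2.725, and power is about 77% with 10 centres per arm and about 91% with 15. The protocol gives no centre-level ICC, assigns 0.025 to colonoscopists and expects less variation between centres. These values are only a sensitivity check under a declared assumption and are not part of this point.

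**Conclusion.** The inconsistency stands. The calculation of 683 lesions and 20 colonoscopists per group is sound on its own inputs; the error is in the sentence that concludes from it. Taken as written, that sentence supplies about half of the required lesions (700 of 1,366). Power would be about 64%, or up to 78% on the most lenient reading, assuming a two-sided 5% test.

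This is the consequence of a literal reading and not a forecast for the trial: 20 per arm gives about 91% and 30 per arm about 98%. Once the probable slip is corrected, one conflict remains that no other section resolves: 20 centres with 40 endoscopists, or 30 centres with 60.

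**What to change.** Correct the last sentence of 3.1.4 and the sentence in 4.2 on selecting 20 endoscopists. Then use one set of numbers in the Summary, section 3, 3.1.4, 4.2 and 4.3.2, with the matching power:

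- **If the larger trial is the plan:** 15 centres and 30 endoscopists per arm, about 2,100 lesions, power about 98% by the protocol's method, with 20 colonoscopists per group named as the minimum required.
- **If the smaller trial is the plan:** 10 centres and 20 endoscopists per arm, about 1,400 lesions, power about 91%, with the Summary, section 3, 4.2 and 4.3.2 changed to agree.

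In 3.1.4, also say whether 35 lesions per colonoscopist is before or after drop-out, and that the test is two-sided. In 4.2, say whether the number to be selected is per group or overall. Any centre-level power figure should appear only as a sensitivity value with its ICC assumption declared.

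The cost is text correction only. Both sizes already stand in the protocol, so neither option adds anything beyond what it describes.

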4. METHODS

4.1 Study parameters/endpoints

4.1.1 Main study parameter/endpoint

- Local recurrence rate (6 months after resection).

4.1.2 Secondary study parameters/endpoints (if applicable)

- Radical (R0) resection rate
- Complication rate
- Number of repeat colonoscopies
- Referral rate to surgery
- Quality of life
- Cost-effectiveness

4.1.3 Other study parameters (if applicable)

Not applicable

4.2 Randomisation, blinding and treatment allocation

Participating centers will be randomized to the *intervention group* vs. *control group*, as detailed in **Figure 1**. To mitigate the effect of contamination, i.e. exchange of knowledge, practical skills between participants, we prefer to randomize centers instead of endoscopists. In each center, two endoscopists will participate in the study. Both the control (n=30 endoscopists) and the intervention group (n=30 endoscopists) will receive an e-learning module regarding the OPTICAL I model focused on optical diagnosis of T1 carcinomas, and assessment of an EMR scar to recognize recurrence. In addition to this, the intervention group will receive an additional EMR training package, consisting of an e-module and a two-day symposium.

We will target our intervention (training) to this specific group because endoscopists at the beginning of their career may be more compliant to implement a change in their practice. An additional questionnaire will be used to provide baseline information regarding total number of endoscopic resections over the past year, resection techniques used (EMR vs ESD), the complication rate (bleeding, perforations) and the referral rate to surgery in order to select 20 endoscopists with comparable experience and endoscopic proficiency. We realize that such selection is associated with difficulty – baseline characteristics among the 2 groups will never be the same. Evaluation of such baseline information is, however, of importance for a meaningful interpretation of the study outcomes.

4.3 Study procedures

4.3.1 Standard optical training and registration (control group)

A training package will be developed to train endoscopists in optical diagnosis based on the features in the OPTICAL I model (Paris classification, location, depression, easy friability and advanced imaging (NBI or chromoendoscopy)). The training will also concern the recognition of recurrence in a post-EMR scar. All participants will register a standardized and pre-defined set of parameters within their endoscopy report for every colonoscopy where a LNPCP >20mm is encountered or removed (Appendix A).

Because size, morphology, site and access to a lesion predict the completeness of resection (SMSA score) {Rutter, 2015}, the difficulty of endoscopic resection will be stratified according to the SMSA score (Figure 1). The features of the SMSA score will also be included in the standardized set of parameters.

Photo documentation will be performed by the endoscopists at the following moments:

1. During lesion assessment
 - a. In white light
 - b. Zoom with advanced imaging (e.g. NBI, I-scan)
2. After performing the EMR
 - a. Scar before adjunctive treatment
 - b. Scar after adjunctive treatment/before adjuvant treatment
 - c. Scar after adjuvant treatment

4.3.2 Training of EMR (intervention group)

[figure not shown]
For the intervention group, an additional training package will be developed to familiarize the therapeutic colonoscopists on the most recent state-of-the-art *knowledge*, and on *technical* and *non-technical* skills {Matharoo, 2014}. We will create modern training tools (e-learning modules, webinars, video training) in addition to hands-on training to systematically train the colonoscopists on endoscopic mucosal resection of LNPCPs.

To develop additional technical skills we will organize hands-on trainings using animal models. At Maastricht UMC+ there is already a tradition on hands-on training (Master-class September 2012, Master-class September 2014). Furthermore, non-technical skills will be trained and assessed using the Endoscopic Non-Technical Skills (ENTS) system (i.e. situation awareness, judgement and decision making, teamwork and leadership skills) {Matharoo, 2014}.

In addition to the registration of the standardized endoscopy report (Appendix A), the 30 endoscopists in the intervention group perform video recording of the first five EMRs they

perform. These video recordings will be evaluated by an expert panel and the endoscopists will receive individualized feedback regarding their EMR procedure.

Figure 1. Flowchart intervention vs. control group STAR-LNPCP study

[figure not shown]

Legend:

* standard documentation of parameters according to the checklist/template.

** Photodocumentation consists of an image of the polyp in white light, followed by zoom together with advanced imaging modality, post-EMR pre adjunctive therapy, after adjunctive therapy, after adjuvant therapy

Figure 2: flowchart of photodocumentation during the different phases of the EMR

4.3.3 Quality of life questionnaires

In both groups, we will assess the impact of performing endoscopic resection for LNPCPs on the patient's quality of life (QoL). Because a validated questionnaire is not yet available, we will adapt the Medical Outcomes Study Short Form 36 {McHorney, 1993;Ware, 1992} and a colorectal-specific European Organisation for Research and Treatment of Cancer (EORTC) QoL questionnaire {Theodoropoulos, 2013}. Questionnaires will be applied at two or three time points, depending on logistics in the particular hospital. When the LNPCP is resected during the index colonoscopy, the patient receives the first questionnaire after this procedure and the second questionnaire after 6 months. When the LNPCP is not resected during the index colonoscopy, but during a new scheduled intervention colonoscopy, the patient receives the first questionnaire after the index colonoscopy, the second questionnaire after the intervention colonoscopy and the third questionnaire after 6 months (when surveillance colonoscopy takes place).

4.3.4 Data inclusion

All endoscopists will perform at least 35 consecutive endoscopic resections of LNPCPs. During the procedure, a tattoo will be placed 2 cm distal of the lesion at the same side, to make sure the scar can be found during the surveillance colonoscopy. Six months follow-up data will be collected for all cases. During this surveillance colonoscopy, endoscopists are asked to report whether there is recurrence and how this is treated. In addition, the scar will be photo documented in white light and zoom with advanced imaging (e.g. NBI, I-scan, blue light). Furthermore, the scar will be biopsied, with one biopsy every 5 mm (with the biopsies being presented to the pathology in separate jars).

Beyond this project proposal, we will monitor long-term (36 months) outcomes after endoscopic resection (i.e. local recurrence, referral to surgery). LNPCP patients will receive surveillance colonoscopy according to the Dutch post-polypectomy surveillance guideline {Dekker, 2013}.

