3. STUDY DESIGN

A standard training program will be developed to improve endoscopic detection of LNPCPs, real-time diagnosis of the depth of SM invasion and endotherapy. We will examine the effect of additional training in a multicenter randomized controlled trial. Specifically, we will compare the safety (complication rate) and effectiveness (local recurrence at 6 months follow-up examination) of endoscopic resection in a group of at least 30 endoscopists who are exposed to a systematic training program on advanced endoscopic imaging, pit-pattern recognition and resection techniques vs 30 endoscopists doing regular training. The training package will comprise modern educational tools (e-learning modules, webinars, video-training). Hands-on training will be provided in animal models (ex-vivo).

The period of inclusion and follow-up will be from 2019-2021, where the duration of the individual patient will be 6 months.

A flow diagram of the study design is presented in the figure below.

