5. STATISTICAL ANALYSIS

Baseline characteristics will be reported as proportions (%) for categorical variables and numerical (mean with SD or median with IQR) where appropriate. The primary outcome is the recurrence rate at 6 months after resection (binary variable). Because of the nested study design (multiple patients within a cluster of colonoscopists), a logistic mixed-effects models with a random intercept at cluster level (colonoscopists) will be used. The study group (intervention groups vs. control group), previous experience on endoscopic resection of LNPCPs (questionnaires) and lesion complexity (SMSA score) will be used as main variables in the model. For the secondary outcomes, the same mixed model will be used as for the primary outcome, in which a linear mixed model analysis will be used for numerical outcome variables (number of repeat colonoscopies and number of complications) and logistic mixed model analysis for categorical outcome variables (referral to surgery). In case of missing variables multiple imputation as well as complete case analysis will be performed. IBM SPSS statistics version 25 will be used for the analyses.

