7. ADMINISTRATIVE ASPECTS, MONITORING AND PUBLICATION

7.1 Handling and storage of data and documents

Participating endoscopists will keep a patient identification log at the site.

An electronic case report form (eCRF) will be used to collect the data (i.e. indication for colonoscopy, colonoscopy findings, endoscopic resection technique used, local recurrence rate, number of repeat colonoscopies, complication rate, and number of referrals to surgery). Informed consents and QoL-questionnaires will be send to the executive researcher by the patients and will be stored in Maastricht.

An external PhD-student (executive researcher) will collect the data in the eCRF. Data collection and storage will be done in Castor Data Management System.

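### Lesions enter the outcome set through a decision to resect, made after centre randomisation, that training may influence, and the protocol gives two bases for counting them, so direct referrals to surgery may fall outside the comparison

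*Protocol*

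**What the plan says.** Section 4.2 randomises centres, to limit the exchange of skills between colleagues. Lesions come in afterwards.

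**Base for outcomes.** Section 4.3.4 builds the data set on resections: "All endoscopists will perform at least 35 consecutive endoscopic resections of LNPCPs". Section 5 says "The primary outcome is the recurrence rate at 6 months after resection (binary variable"), so the primary endpoint exists only for a resected lesion.

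**Base for registration.** Section 4.3.1 is wider. All participants register a fixed set of parameters "for every colonoscopy where a LNPCP >20mm is encountered or removed (Appendix A"). Section 4.3.2 carries this registration into the intervention arm.

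**Content of the training.** The Summary hypothesises that "endoscopic and histological diagnosis followed by a therapeutic plan and high-quality endoscopic resection performance will improve outcome". Section 3 describes the trained group as "exposed to a systematic training program on advanced endoscopic imaging, pit-pattern recognition and resection techniques". Section 4.3.2 adds non-technical skills, including judgement and the making of decisions. Section 4.2 is narrower: both arms receive e-learning on optical diagnosis, and the randomised addition is an EMR package (an e-module and a symposium).

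**Referral to surgery.** It is named in the primary objective (2.1.1) and as a secondary endpoint (4.1.2). The data items in 7.1 include "number of repeat colonoscopies, complication rate, and number of referrals to surgery". Section 5 plans "logistic mixed model analysis for categorical outcome variables (referral to surgery"). Section 4.3.4 also lists it among outcomes following endoscopic resection, in its sentence on 36-month follow-up.

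**The concern.** Randomising centres balances, in expectation, the lesions that the two arms encounter. It does not balance the lesions that they resect if the intervention bears on the decision to resect. Section 2 links pre-treatment diagnosis to the route a lesion takes: endoscopic resection, surgery or a specialised centre. A trained endoscopist might send away lesions that a control colleague would resect, or keep lesions that the colleague would send away. Requiring consecutive resections prevents picking among resected lesions, but does not act on the step before.

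Two results are at stake. A recurrence difference could partly reflect case selection instead of better resection. And if referral to surgery is counted only among resected lesions, patients sent to surgery without a resection attempt drop out of an endpoint that belongs to the primary objective.

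**Working it through.** **1. The protocol's own sections side by side**

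- Inclusion base: resections (4.3.4) against lesions encountered or removed (4.3.1). Nothing says which one serves the referral endpoint.
- Adjustment: section 5 uses previous experience and the SMSA score, which 4.3.1 describes as size, morphology, site and access. Pit pattern and suspected invasion, on which section 2 bases the route, are not part of that description. Appendix A records them, but they are not in the model.
- Route: the Appendix A checklist runs from assessment through EMR to surveillance. It has no item for a lesion left unresected or sent elsewhere.

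**2. The protocol's sample size, needed to put the bias in context**

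Inputs from 3.1.4: 20% v 10% recurrence, 90% power, alpha 5% (taken as two-sided), ICC 0.025, m = 35, 10% efficiency loss, 20% drop-out.

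- Unadjusted n per group: 266.
- Design effect: 1 + (35 − 1) × 0.025 = 1.85, and 266 × 1.85 = 492.1.
- 492.1 / 0.90 / 0.80 = 683.5, against the stated 683. The figure reproduces.
- Effective n per group: 683 × 0.90 × 0.80 / 1.85 = 265.8.

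**3. Recurrence with no gain in skill (assumed mixes)**

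The documents give no rate at which lesions are diverted. Assume that a share h of encountered lesions is hard, with recurrence r_h. The others then have r_l = (0.20 − h × r_h)/(1 − h), which gives 20% overall. If the trained arm diverts a fraction f of the hard lesions, the hard share among its resections is h(1 − f)/(1 − hf).

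With h = 0.30 and r_h = 0.40, r_l = 0.08/0.70 = 11.4%:

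| f | Recurrence, trained arm | Spurious difference | Chance of a significant result favouring training (nominal 2.5%) |
|---|---|---|---|
| 10% | 19.4% | 0.6 points | 3.7% |
| 25% | 18.4% | 1.6 points | 6.9% |
| 50% | 16.5% | 3.5 points | 18.2% |

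Other assumed mixes give differences from 0.3 points (h = 0.30, r_h = 0.30, f = 10%) to 3.3 points (h = 0.50, r_h = 0.30, f = 50%). All figures are before SMSA adjustment.

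**4. The opposite direction**

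Keep h = 0.30 and r_h = 0.40, and suppose training truly halves recurrence. If trained centres take on 10%, 25% or 50% more hard lesions, the observed difference is 9.7, 9.3 or 8.7 points, and power falls from 90% to 88%, 85% or 79%.

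**5. Referral to surgery under the two bases (assumed rates)**

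Let d be the share of encountered lesions referred directly and r the referral rate among resected lesions. Over all encountered lesions, the rate is d + (1 − d) × r.

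- r = 8% in both arms, d = 5% control and 10% trained: 0.05 + 0.95 × 0.08 = 12.6% and 0.10 + 0.90 × 0.08 = 17.2%. The resected-only comparison shows 8% v 8%.
- r = 8% v 4%, same d: 12.6% v 0.10 + 0.90 × 0.04 = 13.6%. The resected-only comparison shows 8% v 4%, so the direction reverses.
- r = 8% v 4%, d = 5% in both arms: 12.6% v 0.05 + 0.95 × 0.04 = 8.8%. No reversal.

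In the second case the direction turns once d in the trained arm exceeds (0.126 − 0.04)/0.96 = 9.0%.

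**The case against.** A reader might infer that direct referrals to surgery are lost. The protocol does not show that. Section 4.3.1 registers encountered lesions, 7.1 collects the number of referrals, and the minimum of 35 resections in 4.3.4 does not in itself confine the referral endpoint. The wording in 4.3.4 that places referral after resection concerns long-term follow-up. Figure 1 is not in the text available and may show where lesions enter and leave.

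A reader might also infer that training does change which lesions are resected. That is plausible, not established. Under 4.2 both arms are trained in optical diagnosis of T1 carcinomas, and 4.3.1 covers depression and advanced imaging for controls as well. Sections 3 and 4.3.2 describe a wider contrast, but neither gives the size or direction of any shift.

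Three further objections have weight. Section 2 names location, size and shape as the most common recurrence factors, and SMSA covers much of that. Better selection can be read as part of the programme's effect, since the Summary includes diagnosis and planning in the hypothesis. And an endpoint's denominator is often left to a statistical analysis plan.

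What survives is narrower. Cases are still formed after allocation, by a decision within the training's reach, and SMSA does not cover suspected invasion. An analysis plan can choose a denominator, but it cannot recover the route of unresected lesions if that was never recorded.

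**Conclusion.** The point holds as a risk that the protocol leaves open. The outcome set is conditioned on a post-randomisation decision that the training may influence, and sections 4.3.1 and 4.3.4 give different bases. The arms may therefore differ in lesion selection, in an unknown direction, and SMSA adjustment removes only part of this. Direct referrals may fall outside the surgery comparison.

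On the assumed mixes, the crude bias in recurrence is about 0.3 to 3.5 points of the planned 10, so selection alone would not produce the targeted effect there. Referral to surgery is more exposed, because its direction can reverse under modest assumed differences in direct referral. None of the diversion or direct-referral rates comes from the documents. The figures show what could happen and are not estimates of what will. The sample size calculation itself reproduces.

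**What to change.** In sections 4.3.4 and 5:

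1. Use the 4.3.1 register of all consecutive encountered LNPCPs as the inclusion log. Record each lesion's route: resected, surgery, referred elsewhere or no treatment.
2. Analyse referral to surgery over all encountered LNPCPs, with or without a resection attempt. Show direct and post-resection referrals separately.
3. Report by arm the proportion resected, and the SMSA and optical-diagnosis mix of resected and unresected lesions.
4. Keep recurrence among resected lesions as the primary endpoint. Any recurrence analysis over all encountered lesions should be supportive only, because counting every surgical referral as a failure is a debatable choice of estimand.
5. Describe optical diagnosis by arm, or use it only in a sensitivity analysis. It is recorded after allocation by the endoscopist and training may alter it, so it should not be a main adjustment.

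The cost is one disposition field in the eCRF and a little more analysis. No clinical rule and no primary endpoint changes.
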